9.2 Recording and Reporting AEs and SAEs

Adverse Events:

All AEs occurring from the time of consent to end of trial participation, must be recorded in the AE eCRF page as well as the participant's medical notes.

Events which are due to the symptomatic deterioration of the participant, and which are expected for participants who have CLAD progression, do not need to be reported as AEs. These events will be recorded in the participant record and will be reported in the eCRF, but not as AEs.

All adverse events which are not associated with the deterioration of the participant or their non-response to treatment will be recorded as AEs, both for participants in the ECP treatment group and also for those in the SOC group. These events include the following:

- Transient fever
- Transient hypotension
- Dizziness / Pre-Syncope
- Nausea
- Vomiting
- Loss of appetite
- Headache
- Fatigue
- Minor photosensitivity reactions
- Local site infections associated with peripheral or central venous catheterisation
- Other Infections of all types: Bacterial Fungal Viral
- Worsening of any baseline medical condition eg hypertension, diabetes, gastro-oesophageal reflux
- Need for blood transfusion
- Need for platelet transfusion

This list is not exhaustive and any other AE which, in the opinion of the investigator is not due to the progression of CLAD, should be reported as an AE.

Serious Adverse Events and Serious Adverse Reactions:

All SAEs occurring from point of consent to end of trial participation (end of the last trial related assessment) must be reported to NCTU on an SAE form and recorded in the AE eCRF page and recorded as serious.

All SARs occurring from the time of first ECP treatment up until the last trial related assessment for the participant at week 24 must be reported to NCTU on an SAE form and also recorded in the AE eCRF page and recorded as serious. All participants in the ECP arm must be followed up for a minimum of 4 weeks after the last ECP treatment.

Following this defined active monitoring period for SARs, investigators are still required to report any SARs or SUSARs they become aware of for all trial participants for the duration of the study (i.e. up until LPLV).

An unscheduled hospitalisation, with any of the following causes, will need to be reported as an SAE:

- Systemic infection associated with central venous catheter use
- Systemic infections associated with peripheral cannulation
- Sepsis of any cause
- Pulmonary embolus
- Myocardial infarction
- Heart failure
- Renal failure new onset or significant deterioration of existing renal dysfunction needing renal replacement therapy
- Allergic reaction to Methoxsalen
- Severe photosensitivity reaction
- New onset cataracts
- New onset malignancy including skin malignancy
- Inability to secure suitable vascular access despite all reasonable attempts

This list is not exhaustive and any other SAE which, in the opinion of the investigator is not due to the progression of CLAD, should be reported as an SAE and an SAE form completed.

All SAEs/SARs must be reported to NCTU on an SAE Form and emailed to NCTU via secure email to the [contact] circulation list as soon as possible and within **24 hours** of staff becoming aware of the event.

Preliminary reporting to NCTU via email or telephone is acceptable in order to meet the 24 hour reporting timeline, where circumstances do not allow for immediate completion of the SAE form. All initial SAE reporting must be reported on an initial SAE form and all subsequent information should be provided on the follow-up SAE form. However, the SAE form should be completed and submitted as soon as possible after the initial notification in order to comply with reporting timelines.

For sites where the ECP unit falls within a different trust to the research team, robust systems must be in place to ensure that any SAEs occurring during delivery of ECP treatment/while the participant is in the care of the ECP unit must be reported within these timescales to avoid deviations and allow for prompt onward reporting to regulatory bodies by sponsor if required.

The ECP team must ensure that the research team (including the PI) are notified of the SAE via email as soon as possible and within 24 hours of becoming aware. The central trial management team must also be copied in to this email via [contact]. This will ensure that the reporting timescales are met.

The research team will then commence completion of the SAE form with all information available at that time and send this to [contact] as soon as possible.

For each SAE the following information will be collected:

- Full details in medical terms and case description.
- Event duration (start and end dates, if applicable).
- Action taken.
- Outcome.
- Seriousness criteria.
- Causality in the opinion of the chief investigator.

Any change of condition or other follow-up information should be submitted to NCTU at [contact] as soon as it is available or at least within 24 hours of the information becoming available. Events will be followed up until the event has resolved or a final outcome has been reached.

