2.2 Secondary Objectives

To determine how the treatment strategies of ECP therapy plus SOC and SOC alone affect the following outcomes over a 24-week period:

- Change in rate of decline in lung allograft function between before randomisation (available from clinical records) and up to 24 weeks after randomisation, measured by change in FEV1 and FVC (litres/month).
- Absolute change in lung allograft dysfunction from baseline to 24 weeks, measured by FEV1 and FVC (litres).
- Change in exercise capacity from baseline to 24 weeks measured by distance walked (metres) during a 6-minute walk test.
- Change in disease severity from baseline to 24 weeks measured by ISHLT CLAD Stage (1-4).
- Change in health-related quality of life from baseline to 24 weeks measured by SF-36 v2 and EQ-5D-5L.
- Survival at 24 weeks after randomisation (end of study).
- Adverse events (AEs) and Serious adverse events (SAEs) from randomisation to 24 weeks.

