5.3.3 Blinding

This trial is unblinded. Study participants, clinicians and the NCTU team will be aware of treatment allocation. The Statistical Analysis Plan (SAP) will be developed by statisticians who are unaware of

treatment allocation and will be finalised and signed-off prior to unblinded data being reviewed by the DMC. The SAP will contain full details of the final analyses, with details of who will perform these analyses. Trial statisticians will have access to unblinded data for the purposes of creating DMC reports. No other members of the research team will have access to the unblinded data contained in closed DMC reports, unless the DMC request that unblinded information is released. In the case that a major amendment is proposed to the SAP, this will be approved by an appropriate blinded independent statistician (the independent Trial Steering Committee statistician or an appropriate senior member of the Biostatistics Research Group).

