5.4.3 Routine Data Collection for all participants

The following routinely collected information will be collected **at each assessment** time point (4, 8, 12, 16, 20 and 24 weeks):

- Changes to CLAD related symptoms.
- Changes to medication or non-drug therapy.
- Changes to routine clinical care.
- Any changes in treatment or new surgical interventions.
- Change in ISHLT CLAD stage.
- Additional clinic visits, urgent and unscheduled clinical assessments, or hospital admissions since previous assessment

The following routine clinical assessment results will be collected (preferably day of assessment):

- Most recent routine bloods (FBC, U&E's, LFT's).
- Most recent chest X-ray.
- Most recent PFT spirometry FEV1/FVC.
- Physical assessments.

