9.7 Notification of Deaths

Fatal SUSARs will be reported within 7 days to REC and MHRA. Monitoring of all other deaths will occur via the TMG, IDMEC and the TSC.

All Participant deaths will need to be reported as SAEs, with the reason for death identified on the SAE form and recorded in the eCRF. The only exception to this is death due to progression of CLAD which will be reported in the eCRF, but not as an SAE.

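### The AE/SAE outcome omits events that unblinded investigators attribute to CLAD progression, so the between-arm harm comparison rests on a filter expected to differ by arm; the size cannot be fixed from the protocol

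*Protocol*

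**What the plan says.** Protocol 2.2 lists "Adverse events (AEs) and Serious adverse events (SAEs) from randomisation to 24 weeks" among the outcomes on which the two strategies are compared. Section 10.2 places the safety analysis in all recruited patients.

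Four statements decide what enters that outcome:

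- 9.2, on AEs: events from symptomatic deterioration "which are expected for participants who have CLAD progression, do not need to be reported as AEs". They are kept in the notes and "will be reported in the eCRF, but not as AEs".
- 9.2, next paragraph: "All adverse events which are not associated with the deterioration of the participant or their non-response to treatment will be recorded as AEs". This also sets aside events linked to non-response.
- 9.2, after the list of hospitalisation causes: "any other SAE which, in the opinion of the investigator is not due to the progression of CLAD, should be reported as an SAE". By implication, a serious event that is not listed and is judged due to progression is not reported.
- 9.7, on reporting deaths as SAEs: "The only exception to this is death due to progression of CLAD".

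Another sentence in 9.2 requires all SAEs from consent to the end of participation to be reported, with no exception, and 9.1 counts any death or inpatient hospitalisation as serious.

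On who decides, 5.3.3 says: "Study participants, clinicians and the NCTU team will be aware of treatment allocation". No arm-blind review of the attribution to CLAD progression is described. Outside the AE/SAE data, 5.4.3 collects at every assessment "Additional clinic visits, urgent and unscheduled clinical assessments, or hospital admissions since previous assessment".

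**The concern.** Exempting expected disease progression from expedited reporting is ordinary. The difficulty is that the same exemption also defines the data for an outcome compared between randomised arms. What is removed is progression of the disease that ECP is meant to slow, and 9.2 extends the removal to non-response, which is close to the failure side of the primary endpoint (7.3). If ECP works, the number of events removed differs by arm.

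At stake is how the harm table reads. With accurate attribution, it shows ECP's added events without any accompanying fall in progression-related admissions. With attribution that leans one way by arm, the recorded difference can move in either direction. The conflicting sentences add a further risk: two sites could file the same admission differently and each be following 9.2.

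**Working it through.** The protocol states no AE, SAE or admission rate, so there is no figure of its own to reproduce. The check has four steps.

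**1. What the exclusion can reach.** Section 9.2 names infections of all types and local catheter-site infections as AEs in both arms. It names unscheduled hospitalisation for sepsis of any cause, for systemic infection related to a catheter or cannula, and for heart failure as SAEs. Investigator opinion governs the remainder, mainly unlisted respiratory deterioration and the admissions it causes. It also governs whether an infection, or progression, was the cause of a given admission.

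**2. Differential removal.** Inputs from 10.1: 90 patients randomised 1:1, so 45 per arm; response 30% on SOC and 55% on ECP. Assumption: non-response stands in for progression.

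- SOC non-responders: 0.70 × 45 = 31.5
- ECP non-responders: 0.45 × 45 = 20.25
- Ratio of events removed, at equal event rates per non-responder: 31.5 / 20.25 = 1.56

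**3. Effect on the ECP-to-SOC ratio.** Assumptions, none of them in the protocol: k = 0.5 to 1 progression events per non-responder; b = 0.5 to 2 other events per participant; 0.2 extra other events per ECP participant. Every progression event is excluded and every other event is recorded.

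- All events, ECP: 0.45k + b + 0.2
- All events, SOC: 0.70k + b
- Recorded ratio: (b + 0.2) / b

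| k | b | All events, ECP | All events, SOC | All-event ratio | Recorded ratio |
|---|---|---|---|---|---|
| 0.5 | 2 | 0.225 + 2.2 = 2.425 | 0.35 + 2 = 2.35 | 1.03 | 2.2 / 2 = 1.10 |
| 1 | 2 | 0.45 + 2.2 = 2.65 | 0.70 + 2 = 2.70 | 0.98 | 2.2 / 2 = 1.10 |
| 0.5 | 0.5 | 0.225 + 0.7 = 0.925 | 0.35 + 0.5 = 0.85 | 1.09 | 0.7 / 0.5 = 1.40 |
| 1 | 0.5 | 0.45 + 0.7 = 1.15 | 0.70 + 0.5 = 1.20 | 0.96 | 0.7 / 0.5 = 1.40 |

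The gap between the two ratios is smallest in the first row and largest in the last.

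**4. Attribution alone.** Suppose the same true risk of 30% in both arms, so 0.30 × 45 = 13.5 events each (assumed). Recorded events are 13.5 × (1 − share attributed to CLAD).

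- 50% attributed in both arms: 6.75 SOC, 6.75 ECP
- 70% SOC, 30% ECP: 13.5 × 0.30 = 4.05 SOC, 13.5 × 0.70 = 9.45 ECP
- 30% SOC, 50% ECP: 13.5 × 0.70 = 9.45 SOC, 13.5 × 0.50 = 6.75 ECP

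With no true difference, the sign of the recorded difference follows the attribution.

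**The case against.** The strongest reply is that progression is the efficacy result. The primary endpoint, FEV1 and FVC change, CLAD stage, walk distance, quality of life and survival already measure it, and counting it again as harm would mix the two. Nothing is lost: excluded events go into the eCRF and admissions are collected at each assessment. Section 10 defers analysis detail to a separate statistical analysis plan, which may contain all-cause tables.

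Much of this stands. The exemption is not an error in itself, and with accurate attribution the recorded ratio is a fair answer to a narrower question about events other than progression. It does not settle the point, because the recording rule and the outcome definition are protocol text. They conflict with each other, and the protocol nowhere commits to an all-cause comparison of events or admissions.

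A reader might infer more than the document supports:

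- That an infected or septic ECP participant could simply be filed as progression. Those causes are named as reportable in 9.2, and 5.5 requires investigators to separate progressive CLAD from infection before declaring non-response.
- That deaths go uncompared. Survival at 24 weeks is a secondary outcome with no restriction by cause.
- That the monitoring committee would see only filtered counts. Section 9.7 sends deaths other than fatal SUSARs to the IDMEC, and the contents of its tables are not specified.

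**Conclusion.** The point holds in a limited form. The stated AE/SAE outcome depends on an attribution made with knowledge of the arm, over a category that should differ by arm if ECP works, and the reporting sentences in 9.2 and 9.7 contradict one another. The practical exposure is unlisted respiratory deterioration and admissions.

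The 1.56-fold differential removal rests on the protocol's assumed response rates, on non-response as a proxy for progression, and on equal event rates per non-responder. The proxy is loose, since 7.3 needs only a loss of more than 10% in FEV1 or FVC at 24 weeks. The effect on the harm ratio could be small (1.03 against 1.10) or material (0.96 against 1.40), and the protocol gives no event rates to choose between them.

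It is tempting to conclude that the comparison is biased against ECP. That does not follow: heavier removal from SOC holds only if ECP slows progression, and attribution could push the other way. The change is worth making because it is cheap, not because a large bias has been shown.

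**What to change.** Keep the exemption for SAE and expedited reporting. Then:

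- Reconcile the all-SAEs sentence in 9.2 with the exceptions in 9.2 and 9.7, and use one wording for the AE exception.
- In 2.2, 9.2 and 10.2, commit to comparing by randomised arm, beside the AE/SAE tables and in the closed report to the monitoring committee, all unscheduled hospital admissions and all recorded events, whatever their attribution to CLAD.
- Show events attributed to CLAD progression as a sub-row by arm, and cross-refer all-cause deaths to the survival outcome.

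The data are already in the eCRF, so sites have no extra SAE reporting. The cost is a short paragraph and more table rows. The safety tables become longer and mix disease with treatment events, which the sub-row separates.

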9. PHARMACOVIGILANCE

9.1 Definitions

Term	Definition
Adverse Event (AE)	Any untoward medical occurrence in a participant to whom a medicinal product has been administered, including occurrences which are not necessarily caused by or related to that product.
Adverse Reaction (AR)	
An untoward or unintended response in a participant to an investigational medicinal product which is related to any dose administered to that participant.
 
The phrase “response to an investigational medicinal product” means that a causal relationship between a trial medication and an AE is at least a reasonable possibility i.e. the relationship cannot be ruled out.
 
All cases judged by either the reporting medically qualified professional or the Sponsor as having a reasonable suspected causal relationship to the trial medication qualify as adverse reactions

Reference Safety Information (RSI)	The RSI is a list of medical terms detailing the ARs that are expected for an IMP and must be referred to when assessing a SAR for expectedness.
Serious Adverse Event (SAE)	
A serious adverse event is any untoward medical occurrence that:
 
 • Results in death • Is life-threatening* • Requires inpatient hospitalisation or prolongation of existing hospitalisation • Results in persistent or significant disability/incapacity • Consists of a congenital anomaly or birth defect • Other important medical events that jeopardise the participant or require intervention to prevent one of the above consequences 
*Life-threatening refers to an event in which the participant was at immediate risk of death at the time of the event; it does not refer to an event which hypothetically might have caused death if it were more severe.

Serious Adverse Reaction (SAR)	An adverse event that is both serious and, in the opinion of the reporting Investigator, believed with reasonable probability to be due to one of the trial treatments, based upon the information provided.
Suspected Unexpected Serious Adverse Reaction (SUSAR)	A serious adverse reaction, the nature and severity of which is not consistent with the approved Reference Safety Information.

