9.6 Responsibilities

Principal Investigator or delegate

- Checking for AEs and ARs when participants attend for treatment or follow-up
- Using medical judgement in assigning seriousness and causality on events
- Ensuring that all SAEs and SARs, are recorded and reported to the Sponsor within 24 hours of becoming aware of the event and provide further follow-up information as soon as available.
- Ensuring that AEs and ARs are recorded and reported to the Sponsor in line with the requirements of the protocol.

Chief Investigator

- Clinical oversight of the safety of trial participants, including an ongoing review of the risk/benefit.
- Using medical judgement in assigning seriousness, causality and expectedness of SAEs where it has not been possible to obtain local medical assessment.
- Using medical judgement in assigning expectedness to SARs in line with the RSI.
- Immediate review of all SUSARs.
- Review of specific SAEs and SARs in accordance with the trial risk assessment and protocol.
- Review/assignment of Medical Dictionary for Regulatory Activities (MedDRA) preferred terms System Organ Class coding for all SAEs and SARs.
- Confirming what changes to RSI are required as part of the annual review process of the SmPC.
- Preparing the clinical sections and final sign off of the Development Safety Update Report (DSUR).

Sponsor

- Data collection and verification of AEs, ARs, SAEs, SARs and SUSARs onto a database (may be delegated to NCTU, according to the delegation agreement).
- Reporting safety information to the independent oversight committees for the ongoing assessment of the risk/benefit ratio throughout the life of the trial (may be delegated to NCTU).
- Assessment of expectedness of any SUSARs (delegated to the CI)
- Expedited reporting of SUSARs to the Competent Authority (CA) and REC within required timelines
- Notification of all investigator sites of any SUSAR that occurs (may be delegated to NCTU).
- Reviewing RSI at least annually and notification of PIs of any required updates (may be delegated to NCTU)
- Preparing tables and other relevant information for the DSUR in collaboration with the CI and ensuring timely submission to the MHRA and REC (may be delegated to NCTU)

TSC/DMC/TOC

- Review of safety data collected to date to identify any trends

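### The SAE data list in Protocol 9.2 records only the chief investigator's causality opinion, which contradicts 9.1 and 9.6, where the reporting investigator's opinion counts

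*Protocol*

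**What the plan says.** Section 9.2 (Recording and Reporting AEs and SAEs) lists what is collected for each SAE: case description, dates, action, outcome, seriousness criteria and, last, "Causality in the opinion of the chief investigator". No item asks for the opinion of the site.

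Section 9.1 (Definitions) places the judgement elsewhere. A serious adverse reaction is a serious event "in the opinion of the reporting Investigator, believed with reasonable probability to be due to one of the trial treatments". The entry for adverse reactions adds that "All cases judged by either the reporting medically qualified professional or the Sponsor as having a reasonable suspected causal relationship" to the trial medication qualify.

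Section 9.6 (Responsibilities) gives the principal investigator or delegate the task of "Using medical judgement in assigning seriousness and causality on events". The chief investigator's corresponding task is limited: "Using medical judgement in assigning seriousness, causality and expectedness of SAEs where it has not been possible to obtain local medical assessment".

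Section 9.4 (Recording and Reporting SUSARs) requires sites to report all reactions and suspected reactions, using the SAE route of 9.2. It gives the expectedness assessment to the chief investigator on the sponsor's behalf.

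**The concern.** Section 9.2 tells sites and the trials unit what an SAE record contains. If it is followed as written, the physician who saw the patient has no listed place to state a suspicion, although 9.1 and 9.6 make that suspicion decisive.

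Classification as a SAR decides whether an event goes on to expectedness review and possible expedited reporting as a SUSAR. If the only listed causality opinion comes from the person who then judges expectedness, both steps rest on one view. The rule in 9.1 that either party's suspicion is enough could not be shown from the listed data to have been applied.

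**Working it through.** No arithmetic applies. The check sets the sections side by side and asks what each gives when the two opinions agree or differ.

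**Whose causality opinion counts**

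| Section | Reporting investigator | Chief investigator or sponsor |
|---|---|---|
| 9.1, adverse reaction | Sufficient alone | Sponsor's view sufficient alone |
| 9.1, serious adverse reaction | Named as the deciding opinion | Not mentioned |
| 9.6 | Assigns causality | Chief investigator only as fallback |
| 9.2, SAE data items | No item | Chief investigator's opinion is the only item |

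**What follows for a serious event.** The chief investigator is taken here to speak for the sponsor. That is an assumption: 9.4 and 9.6 delegate expectedness to the chief investigator but do not say the same of the sponsor's causality view.

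| Reporting investigator | Chief investigator | 9.1, adverse reaction rule | 9.1, serious reaction definition | 9.2 item alone |
|---|---|---|---|---|
| Suspects | Suspects | Reaction | SAR | Related |
| Suspects | Does not | Reaction | SAR | Not related |
| Does not | Suspects | Reaction | Not met by this wording | Related |
| Does not | Does not | No reaction | Not met | Not related |

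The second row is the one that matters. Both entries in 9.1 call the event a reaction, but the single item in 9.2 records it as unrelated. The third row shows that the two entries in 9.1 also differ from each other when only the chief investigator or sponsor suspects a link. A corrected 9.2 item should therefore state the rule that either opinion is enough.

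**Does 9.4 repair this?** Only in part. It obliges the site to send in a suspected reaction, so the site's suspicion should start a report. But it sends that report through the method in 9.2, whose item list does not hold the suspicion. The minimum information that starts the SUSAR clock includes a causality assessment, without saying whose.

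**What is not lost.** An event in the second row is still an SAE and must still be reported within 24 hours. What is at risk is its classification as a reaction, not the report of the event.

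**The case against.** The strongest reply is that the protocol taken as a whole protects the site's view. Section 9.6 obliges the principal investigator to judge causality, 9.4 obliges the site to report suspected reactions, and under 9.1 a contrary view from the chief investigator cannot cancel the reporter's suspicion. The SAE form is not among the documents and the safety reporting diagram in Appendix 4 is not shown, so either may already ask for the principal investigator's opinion. All of this stands, and it limits the consequence to something that could happen. It does not remove the contradiction, because 9.2 is the operative data list and names a different person.

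A reader might also infer a second fault. Section 9.2 introduces its examples with "An unscheduled hospitalisation, with any of the following causes, will need to be reported as an SAE", and the examples include "New onset malignancy including skin malignancy" and new cataracts, which need not lead to admission. It is tempting to conclude that such harms count as serious only if the patient is admitted. The documents do not support that. The list does not say that only admissions count. The same section requires every SAE to be reported and declares the list open-ended. Section 9.1 still makes serious "Other important medical events that jeopardise the participant or require intervention to prevent one of the above consequences". The list does not contradict 9.1; at most its opening sentence could be misread. Making listed items reportable as SAEs whether or not they meet 9.1 would be a preference, not a correction.

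Nor can the problem be sized from the 13% line-sepsis rate in the 60-patient series cited in section 1.2. That section says these infections were confined to patients with long-term indwelling catheters, and 8.2.2 prefers peripheral access. Applying the rate to the whole ECP arm is unsupported.

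**Conclusion.** The causality item in 9.2 is wrong as written: it contradicts 9.1 on whose opinion defines a reaction and 9.6 on who assigns causality. The defect matters when the site suspects a link and the chief investigator does not. In that case literal use of 9.2 records a site-suspected reaction as unrelated, and it may miss expectedness review and SUSAR reporting.

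The number of such events cannot be estimated from the documents. The consequence assumes that the SAE form follows the list in 9.2; if the form already records the reporting investigator's opinion, only the protocol text needs correcting. The finding does not extend to the hospitalisation list.

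**What to change.** In 9.2, replace the last SAE data item with: *Causality in the opinion of the reporting investigator (PI or delegate), with the chief investigator's/sponsor's opinion recorded separately; the event is a suspected reaction if either suspects it.* This brings 9.2 into line with the either-party rule in 9.1 and the division of roles in 9.6. Check that the SAE form and the Appendix 4 diagram carry both opinions.

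Optionally, add one line after the hospitalisation examples saying that they do not limit the seriousness criteria in 9.1.

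The cost is protocol wording and perhaps one form field, and possibly a few more events classed as SARs.
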